CDM	Clinical Data Manager
CFR	Code of Federal Regulations
CRA	Clinical Research Associate
CRO	Contract Research Organization
DCF	Data Clarification Form
DVM	Data Validation Manual
EC	Ethics Committee
e-CRF	Electronic Case Report Form
EDC	Electronic Data Capture
EDTA	Ethylenediaminetetraacetic Acid
ET	Early Termination
ETDRS	Early Treatment of Diabetic Retinopathy Study
FDA	Food and Drug Administration
F/U	Follow Up
GCP	Good Clinical Practice
HIPAA	Health Insurance Portability and Accountability Act
HAV	Hepatitis A
HIV	Human Immunodeficiency Virus
ICF	Informed Consent Form
ICH	International Conference on Harmonisation
ICS	Inferior Corneal Staining
IgG	Immunoglobulin G
IgM	Immunoglobulin M
IND	Investigational New Drug
IOP	Intraocular Pressure
IP	Investigational Product
IRB	Institutional Review Board
ITT	Intent-to-Treat
IUD	Intrauterine Device
KCS	Keratoconjunctivitis Sicca
LASIK	Laser-assisted in situ keratomileusis
LDPE	Low Density Polyethylene
LOCF	Last Observation Carried Forward
LogMAR	Minimum Angle of Resolution

MCMC	Markov Chain Monte Carlo
MedDRA	Medical Dictionary for Regulatory Authorities
MW	Molecular Weight
N	Number
ODS	Ocular Discomfort Score
OPI	Ocular Protection Index
OSDI	Ocular Surface Disease Index
OTC	Over the Counter
OU	Oculus Uterque (Each eye or Both eyes)
PI	Principal Investigator
PK	Pharmacokinetics
PP	Per Protocol
SAE	Serious Adverse Event
SAP	Statistical Analysis Plan
SDC	Statistics and Data Corporation, Inc.
SEC	Self-Evident Correction
STT	Schirmer's Tear Test
TFBUT	Tear Film Break Up Time
TM	Trademark
US	United States
VA	Visual Acuity
VAS	Visual Analog Scale
WOCF	Worst Observation Carried Forward

1 INTRODUCTION

Dry eye is a complex disease that results in symptoms of discomfort, visual disturbance, and tear film instability. It is accompanied by increased osmolarity of the tear film and inflammation of the ocular surface. Estimates of the prevalence of dry eye vary considerably, depending on the criteria used to define the syndrome, but in the U.S., as many as 3.2 million women and 1.7 million men over the age of 50 have dry eye, with a projected 40% increase in number of patients affected by 2030¹⁻³. With the aging population in the United States and other countries of the developed world, and with increasing computer use, dry eye is expected to become more prevalent and finding a treatment is becoming more important⁴.

HL036 ophthalmic solution is a molecularly engineered TNF receptor 1 (TNFR1) fragment (HL036337). Molecule fragmentation and engineering techniques are applied for enhanced tissue distribution, increased stability and potency.

HL036337 is a TNFR1 fragment composed of 171 amino acids, from 41 ~ 211 residues of TNFR1 outside domain and a methionine residue added at the N-terminal.

HL036337 is a protein molecularly engineered by amino acid substitution of the 29th leucine, 53rd histidine, 56th histidine, 58th arginine, 59th histidine, and 122nd lysine with valine, methionine, phenylalanine, proline, glycine, and asparagine respectively.

HL036 eye drops demonstrated potent anti-inflammatory effects in a carrageenan-induced acute in vivo model of inflammation, and significant efficacy in a collagen-induced arthritis model. HL036 ophthalmic solution has also been shown to cause statistically significant clinical improvements in a dry eye animal model.

1.1 NONCLINICAL STUDIES

[REDACTED]

1.2 PREVIOUS CLINICAL STUDIES

There is no information on the clinical efficacy of HL036 in dry eye.

One Phase 1 clinical trial aimed to assess the safety, local tolerance, and pharmacokinetic properties of HL036 by topical ophthalmic instillation of HL036 twice in one day (12 hours apart) into left eyes of healthy male volunteers, while right eyes received vehicle placebo.

One drop (40 μ l) of HL036 at either the 0.5 mg/mL or 5 mg/mL concentration topically instilled twice to healthy male volunteers resulted in no clinically significant systemic absorption observed in any of the subjects. Safety and local tolerance assessment results showed no clinically significant observations.

1.3 STUDY RATIONALE

HL036 ophthalmic solution is a molecularly engineered tumor necrosis factor (TNF) receptor 1 (TNFR1) fragment (active pharmaceutical ingredient also denoted as HL036337). Molecule fragmentation and engineering techniques are applied for enhanced tissue distribution, increased stability and potency.

Anti-TNF molecules have been approved for rheumatoid arthritis, psoriasis, ankylosing spondylitis, ulcerative colitis, and Crohn's diseases. They are also prescribed for off-label use for uveitis, dry eye disease, macular degeneration, sciatic neuralgia, chronic obstructive pulmonary diseases and asthma.

The role of TNF as a major cytokine in dry eye provides a rationale for use of TNF inhibitors in this disease. However, the majority of TNF inhibitors are antibody-based with a large molecular size (~150 kDa) that limits tissue penetration. Considering the limited ocular distribution and excessive toxicity of TNF-inhibitor therapies administered systemically, HL036 Ophthalmic Solution was developed as a TNF-inhibitor with increased penetration and distribution and minimal systemic side effects.

2 STUDY OBJECTIVES

The objective of this study is to compare the safety and efficacy of 0.10% and 0.25% HL036 Ophthalmic Solutions to placebo for the treatment of the signs and symptoms of dry eye.

3 CLINICAL HYPOTHESES

The clinical hypotheses for this study are that 0.10% or 0.25% HL036 Ophthalmic Solution is superior to placebo for the primary endpoints of signs and symptoms, as follows:

- Pre- CAE® inferior corneal fluorescein staining score on the Ora Calibra® scale, measured by mean change from baseline (Visit 2) to Visit 6;
- Pre- CAE® ocular discomfort score on the Ora Calibra® Ocular Discomfort Scale, measured by mean change from baseline (Visit 2) to Visit 6;

4 OVERALL STUDY DESIGN

This is a Phase 2, multicenter, randomized, prospective, double-masked, placebo-controlled, parallel-arm design with block enrollment. Subjects will be randomized to one of the following treatment arms at Visit 2 and will be instructed to follow a BID-dosing regimen:

- HL036 0.25% Ophthalmic Solution (N~50)
- HL036 0.10% Ophthalmic Solution (N~50)
- Placebo, HL036 Ophthalmic Solution (N~50)

This study is multicenter, randomized, prospective, double-masked, placebo-controlled, parallel-arm design with block enrollment. Approximately 150 subjects will be randomly assigned to one of the three treatment groups (1:1:1) to receive either HL036 Ophthalmic Solution (0.10%, 0.25%) or placebo solution as topical ophthalmic drops administered bilaterally BID. Subjects, Sponsor, CRO and site personnel will be masked to treatment assignment.

[figure not shown]
During the screening period, two [REDACTED] exposures to the CAE® will be conducted to ascertain eligibility to enter the study. Those who qualify will be randomized to receive study drug in a double-masked fashion for 56 days. Subjects will self-administer drops twice daily and will complete daily diary assessments as instructed.

At Visits 4 (Day 15), 5 (Day 29) and 6 (Day 57), CAE® exposure will occur, with pre-CAE®, during CAE® (symptoms only) and post-CAE® assessments of ocular signs and symptoms. At Visit 3 only, no CAE® exposure will occur but signs and symptoms will be assessed.

The total number of expected participants, including screen failures, is approximately 375 subjects.

A study flow chart appears below:

Visit 1 (Day -14 ± 1): CAE® Screening	Informed Consent Demographics, Medical/Medication & Ocular History Urine Pregnancy Testing (as needed) Symptom Questionnaires, Visual Acuity Pre-CAE® Eye Evaluations CAE® Exposure Post-CAE® Eye Evaluations
------------------------------------------------------	----------------------------------------------------------------------------------------------------------------------------------------------------------------------------------------------------------------------------------------

Subjects who terminate early during the treatment period will be asked to complete safety assessments prior to commencement of any alternative dry eye therapy (if at all possible). Subjects who are terminated early from the study will not be replaced.

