5.4 EXCLUSION CRITERIA

Individuals who meet any of the following exclusion criteria will not be eligible to participate in the study:

1. Have any clinically significant slit lamp findings at Visit 1 that may include active blepharitis, meibomian gland dysfunction (MGD), lid margin inflammation or active ocular allergies that require therapeutic treatment, and/or in the opinion of the investigator may interfere with study parameters;
2. Be diagnosed with an ongoing ocular infection (bacterial, viral, or fungal), or active ocular inflammation at Visit 1;
3. Have worn contact lenses within 7 days of Visit 1 or anticipate using contact lenses during the study;
4. Have previously had laser-assisted *in situ* keratomileusis (LASIK) surgery within the last 12 months;
5. Have used Restasis® or Xiidra® within 60 days of Visit 1;
6. Have any planned ocular and/or lid surgeries over the study period;
7. Be using or anticipate using temporary punctal plugs during the study that have not been stable within 30 days of Visit 1;
8. Be currently taking any topical ophthalmic prescription (including medications for glaucoma) or over-the-counter (OTC) solutions, artificial tears, gels or scrubs, and cannot discontinue these medications for the duration of the trial (excluding medications allowed for the conduct of the study); the respective wash-out periods are required for the following medications:
 - a) Antihistamines (including ocular): 72 hours prior to Visit 1

- b) Oral aspirin or aspirin-containing products allowed if dose has been stable over past 30 days prior to Visit 1 and no change in dose anticipated during the study period
- c) Corticosteroids or mast cell stabilizers (including ocular): 14 days prior to Visit 1
- d) Any medication (oral or topical) known to cause ocular drying that has not been administered as a stable dose for at least 30 days prior to Visit 1 and during the study
- e) All other topical ophthalmic preparations (including artificial tear substitutes) other than the study drops: 72 hours prior to Visit 1

9. Have an uncontrolled systemic disease;
10. Be a woman who is pregnant, nursing or planning a pregnancy;
11. Be unwilling to submit a urine pregnancy test at Visit 1 and Visit 6 (or early termination visit) if of childbearing potential. Non-childbearing potential is defined as a woman who is permanently sterilized (e.g. has had a hysterectomy or tubal ligation), or is post-menopausal (without menses for 12 consecutive months);

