5.5 WITHDRAWAL CRITERIA

Subjects (or their legally authorized representative) may withdraw their consent to participate in the study at any time without prejudice. The Investigator must withdraw from the study any subject who requests to be withdrawn. A subject's participation in the study may be discontinued at any time at the discretion of the Investigator and/or Sponsor and in accordance with his/her clinical judgment. However, it is encouraged that the Investigator contact the Sponsor, when possible, to discuss possible reasons for

discontinuation prior to withdrawing a subject from the study. When possible, the tests and evaluations listed for the termination visit should be carried out.

HanAll Biopharma, Co., Ltd. and Ora must be notified of all subject withdrawals as soon as possible. HanAll Biopharma, Co., Ltd. also reserves the right to discontinue the study at any time for either clinical or administrative reasons and to discontinue participation by an individual Investigator or site for poor enrollment or noncompliance.

Reasons for which the Investigator or HanAll Biopharma, Co., Ltd. may withdraw a subject from the study include, but are not limited to, the following:

- Subject experiences a serious or intolerable AE
- Subject requires medication prohibited by the protocol
- Subject does not adhere to study requirements specified in the protocol
- Subject was erroneously admitted into the study or does not meet entry criteria
- Subject is lost to follow-up
- Subject becomes pregnant

If a subject fails to return for scheduled visits, a documented effort must be made to determine the reason. If the subject cannot be reached by telephone after two attempts, a certified letter should be sent to the subject (or the subject's legally authorized representative, if appropriate) requesting contact with the Investigator. This information should be recorded in the study records.

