8.4.2 Unscheduled Visits

These visits may be performed in order to ensure subject safety. All procedures performed at an unscheduled visit will be recorded in the source documents and on the

Unscheduled Visit eCRF pages. Any procedure indicated in the eCRF that is not performed should be indicated as “Not done.”

Evaluations that may be conducted at an Unscheduled Visit include:

- Slit-lamp Biomicroscopy;
- Visual Acuity;
- Intraocular Pressure;
- Urine Pregnancy Test;
- Dilated Fundoscopy;
- Assessment of Adverse Events;
- Assessment of concomitant medications and/or treatments; and
- Any other assessments needed in the judgment of the investigator.

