### **9.2 Missing or Inconclusive Data Handling**

The primary efficacy analyses will be performed using Markov Chain Monte Carlo (MCMC) multiple imputation methodology for missing values. An analysis using observed data only will also be performed for the primary efficacy variables. As additional sensitivity analyses, Last Observation Carried Forward (LOCF) methodology and imputation via pattern mixture models will also be used to impute missing data for the analyses of the primary efficacy variables.

For the LOCF analyses of the primary efficacy variables at Day 57 (Visit 6), the last value from the previous visits will be carried forward, matching pre-CAE® or post-CAE® time points. A pre-CAE® time point will never be imputed for a post-CAE® value, and vice versa.

No secondary efficacy endpoints or safety endpoints will be imputed.

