### **15.3 Slit-Lamp Biomicroscopy Examination**

A slit-lamp biomicroscopy examination of the cornea, conjunctiva, anterior chamber, iris, lens, and lid will be performed at each visit, and potentially at an Early Termination Visit. Both pre- and post-CAE® examinations will be made at Visits 1, 2, 4, 5, and 6. The results will be graded as normal, Abnormal Not Clinically Significant (NCS) or Abnormal Clinically Significant (CS). Abnormal findings will be described.

The results will be summarized using counts and percentages for each treatment group at each visit for each eye (study eye and fellow eye). Percentages will be based on the number of subjects in each treatment group with responses. Shift tables for the slit-lamp biomicroscopy parameters will also be provided comparing each follow-up visit to baseline. A subject listing of the slit-lamp biomicroscopy parameters will also be produced.

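### The early-termination visit is undefined: neither co-primary score is required at exit, and the imputation models ignore everything between baseline and Visit 6

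*Protocol*

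**What the plan says.** **What is asked of early leavers.** Protocol Section 4 gives the one explicit instruction, qualified by feasibility: "Subjects who terminate early during the treatment period will be asked to complete safety assessments prior to commencement of any alternative dry eye therapy". Section 5.5 adds: "When possible, the tests and evaluations listed for the termination visit should be carried out". No such list appears. Section 8.3 describes Visits 1 to 6 only, and neither Appendix 1 of the protocol nor SAP Section 4.2 has an early-termination column.

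**Where the visit is named elsewhere.** It is always for a safety test. Protocol Section 5.4 mentions it for pregnancy testing: "Be unwilling to submit a urine pregnancy test at Visit 1 and Visit 6 (or early termination visit) if of childbearing potential". SAP Section 15.3 says the slit-lamp examination "will be performed at each visit, and potentially at an Early Termination Visit", and Sections 15.4 and 15.5 say the same of fundoscopy and IOP. The SAP sections on fluorescein staining and the Ocular Discomfort Scale carry no such addition. Protocol Section 8.4.2 leaves room at unscheduled visits for "Any other assessments needed in the judgment of the investigator".

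**What is collected on schedule.** Both co-primary measures are scored at Visits 3, 4, 5 and 6 (Days 8, 15, 29 and 57). Visit 3 has no chamber exposure: "At Visit 3 only, no CAE® exposure will occur but signs and symptoms will be assessed".

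**How missing Day 57 scores are handled.** SAP Section 9.2 states: "The primary efficacy analyses will be performed using Markov Chain Monte Carlo (MCMC) multiple imputation methodology for missing values". The code in SAP Section 14.1.1 imputes from two variables, baseline and the Visit 6 score, separately by treatment and site. The pattern-mixture sensitivity model regresses Visit 6 on baseline and site using placebo subjects. In the LOCF sensitivity analysis "the last value from the previous visits will be carried forward", matched on pre-CAE or post-CAE time point. An observed-data analysis is also planned.

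**The concern.** A subject who attends an exit visit before starting another therapy can still give an on-study staining grade and discomfort score. Once other therapy starts, those scores cannot be recovered. The protocol itself expects some leavers to move to alternative dry eye treatment, and Section 5.5 lists intolerable adverse events and need for prohibited medication among the reasons for withdrawal. Dropout related to the outcome is therefore plausible.

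Two weaknesses combine. First, collection at exit is left to each site's reading of Sections 4 and 5.5. Second, the primary imputation and the pattern-mixture analysis are specified so that they use no leaver's post-baseline data at all, not even the Visit 3, 4 and 5 scores the trial does collect. A leaver is filled in from subjects with Visit 6 data who share the same baseline score: from the same arm and site under MCMC, and from placebo under the pattern-mixture model. Only LOCF uses a leaver's own course, and then only up to the last scheduled visit.

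**Working it through.** **1. The plan's own figures (protocol 10.3, SAP 6).** Two-sample t-test, two-sided alpha 0.05, 45 per arm, noncentral t:
- Sign, 0.5 / 0.72: power 90.3%.
- Symptom, 0.80 / 1.15: power 90.4%.
- Joint: 0.9² = 81% and 0.9⁴ = 65.6%, stated as 66%.

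All reproduce, and nothing below changes them.

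**2. How many subjects.** 0.10 × 50 = 5 per arm; 3 × 5 = 15 of 150. This is an upper bound for exit scores, because some leavers will be lost to follow-up or withdraw consent.

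**3. How old the last scheduled score can be at exit.** The gaps between scheduled scorings after baseline are:
- Day 1 to 8: 7 days
- Day 8 to 15: 7 days
- Day 15 to 29: 14 days
- Day 29 to 57: 28 days

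The last gap is half of the 56-day treatment period. With Visit 5 at its earliest (29 − 2 = Day 27) and Visit 6 at its latest (57 + 3 = Day 60), it is 33 days.

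**4. Which analyses an exit score would reach as the plan stands.**

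| Analysis | Leaver's data used | Effect of collecting an exit score, no other change |
|---|---|---|
| MCMC (primary) | Baseline, arm, site | None |
| Pattern mixture | Baseline, site | None |
| LOCF | Last earlier visit, time-point matched | Helps, if the score is labelled pre-CAE |
| Observed data | None | None |

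**5. What the documents allow on size.** Two illustrations, both on assumptions that the documents do not supply.

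*Diluted effect.* Take 50 per arm, unchanged SD, and filled-in values for the 10% missing that carry a fraction f of the true difference. The difference is multiplied by 0.9 + 0.1f.
- f = 0: 0.45 and 0.72 units; power 87.2% (sign) and 87.3% (symptom).
- f = 0.5: 90.4% and 90.5%.
- f = 1: 93.0% and 93.1%.

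*Informative dropout in one arm.* If its 5 leavers are truly d units worse than imputed, that arm's mean is off by (5/50) × d.
- d = 0.5: 0.05 units, which is 10% of the 0.5-unit staining difference.
- d = 1.0: 0.10 units, which is 20% of the staining difference and 12.5% of the 0.80-unit discomfort difference.

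**6. Whether the imputation cells can hold more variables.** Assuming 3 equal sites, a treatment-by-site cell has 50/3 ≈ 16.7 subjects, about 15 with Visit 6 data and 1.7 without. The present two-variable normal model has 2 means + 3 variances and covariances = 5 parameters per cell. Adding Visits 3, 4 and 5 gives 5 + (5 × 6)/2 = 20 parameters, more than the subjects in a cell. Adding visits therefore calls for pooling sites.

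**The case against.** **The text does not restrict the exit visit to safety.** A reader might infer that only safety assessments are permitted and that co-primary scores are never taken. The documents do not say so. Section 4 does not exclude efficacy scoring, Section 5.5 asks for termination-visit tests of unstated content, and Section 8.4.2 permits other assessments at the investigator's judgment. What is supported is that the scores are not required and the visit is not defined. The Section 4 flow chart is also incomplete in the copy reviewed, so it cannot be ruled out as a source. This objection stands against the stronger reading. It leaves the gap in both schedules untouched.

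**The primary analysis is not weak because exit scores are missing.** A reader might infer that it is. The MCMC model would ignore an exit score even if one existed, and it draws on observed Visit 6 scores from the same arm and site as well as on baseline. This also stands. It means that collection alone is not a remedy and the models must change too. LOCF would matter more if it were primary, as the protocol synopsis and Section 10.1 still say in places, but SAP Section 1 states that the SAP's methods supersede the protocol's.

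**The size is unproven.** A full unit on staining is about 1.4 of the assumed SD (1.0 / 0.72), no passage supports it, and nothing shows how much of any such shift an exit score would remove. That is correct.

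**Safeguards exist.** Both measures are scored on Days 8, 15 and 29, a diary records symptoms twice daily, and a control-based pattern-mixture analysis probes departure from missing at random. These help only in part. The diary uses a different questionnaire, scored 0 to 5 for both eyes together, and says nothing about staining. The pattern-mixture model imposes an assumption on leavers without looking at their own scores.

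**Conclusion.** The point holds as a gap in definition and in model specification. Neither co-primary score is required at early exit, Sections 4 and 5.5 and the two schedules need to be reconciled, and collection may vary by site. LOCF may carry a score up to 28 days old at exit (33 days before the Visit 6 assessment at the window limits). The MCMC and pattern-mixture models cannot see worsening before withdrawal because they omit all scores between baseline and Visit 6.

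The reach is at most about 15 subjects at the assumed 10% dropout. Under the diluted-effect illustration, power per endpoint stays between about 87% and 93%, against 90% stated. That calculation does not measure bias from informative or unequal dropout. The 0.05 to 0.10 unit shift is what would follow if the 5 leavers in one arm were 0.5 to 1.0 unit worse than imputed. It is not an estimate, and it should not be read as the amount an exit score would recover. The sample size needs no change.

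**What to change.** **Protocol.** Reconcile Sections 4 and 5.5 with Appendix 1 and SAP Section 4.2 by adding an early-termination column. Include fluorescein staining and the Ocular Discomfort Scale under non-CAE conditions, taken where possible before any alternative therapy.

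**SAP, LOCF.** Treat the exit score as a pre-CAE value and carry it forward. SAP Section 9.3 already pairs the non-CAE Visit 3 with the pre-CAE baseline, so there is a precedent.

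**SAP, imputation models.** Add the Visit 3, 4 and 5 pre-CAE or non-CAE scores, which are already collected, to the MCMC and pattern-mixture models. Map each exit score to the nearest scheduled post-baseline visit. Do not enter it as a separate auxiliary variable: a score seen only in leavers is never observed together with Visit 6, so its relation to Visit 6 cannot be estimated. Exit scores do not replace the Day 57 value, so one falling closest to Visit 6 must not fill the Visit 6 slot. State which value is used when the mapped visit already has a score. Mapping assumes that an exit score relates to Day 57 as the scheduled score does, and the SAP should say so. Pool sites in the imputation, with site as a covariate, if the treatment-by-site cells are too small.

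**Cost.** A few minutes per exit visit for at most about 15 subjects, fewer in practice, with no chamber exposure, plus a small protocol and SAP edit. Endpoints, treatment and sample size stay as they are.
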